3.3 Concomitant Medications

Any medication the patient takes other than the study drug, including herbal and other non-traditional remedies, is considered a concomitant medication. The following information must be recorded in the eCRF for each concomitant medication: generic name, route of administration, start date, stop date, dosage and indication. Any change in the dose or regimen of a concomitant medication must be recorded in the eCRF.

3.3.1 Prohibited Concomitant Medications

All prescription, non-prescription, or herbal therapies used to treat constipation or facilitate bowel movements are prohibited during the study, except the Sponsor-supplied rescue medication (see Section 3.3.2).

The following concomitant medications and supplements are prohibited during the study:

- Resolor[®] (prucalopride)
- Opioids intended for chronic use
- Amitiza[®] (lubiprostone)
- Linzess[®]/Constella[®] (linaclotide)

- Lactulose
- Laxatives, except the Sponsor-supplied rescue medication (RM)

Note: There is no indication of any specific safety risk when these generally prohibited agents are used concomitantly with plecanatide; however, appropriate medical caution should be exercised when agents that may aggravate underlying constipation are taken or when agents with similar physiological outcomes (i.e., increased BM frequency) are used together.

3.3.2 Permitted Concomitant Medications

Bisacodyl (Dulcolax®) 5 mg tablets will be supplied as rescue medication (RM) for the study. Patients must only use the Dulcolax® supplied by the Investigator during the study. See Sections 4.4.7 and 6.2 for more information on RM. Drugs given to treat AEs will be allowed.

4 VARIABLES AND METHODS OF ASSESSMENT

4.1 Demographics and Baseline Characteristics

Demographic data, medical history (including ongoing AEs) and previous/concomitant medications recorded in the eCRF of the previous plecanatide core study will be replicated in the eCRF for this open-label study when the patient signs the informed consent and is enrolled into this open-label study. New information or clinically-significant changes since the core trial will be solicited from all patients for appropriate updates to the eCRF for this open-label study.

4.1.1 Disease and Medical History

A complete medical history and GI disease history will be recorded for all plecanatide study-naïve and SP304-20212 patients. Source documentation for previous treatment, diagnosis, and interventions, where available, should be included in the patient's medical record to facilitate source documentation verification. The outcome of the medical history assessment may be recorded as part of the worksheet for evaluation of eligibility and can be added to the patient's medical records.

4.2 Colonoscopy

A colonoscopy is not required to make a diagnosis of IBS or IBS-C. However, there are two clinical settings where a colonoscopy is required during the screening period:

- 1) If a patient has not completed a recommended colonoscopy based on the colon cancer screening and surveillance colonoscopy intervals outlined by the AGA, then a study-related eligibility colonoscopy can be authorized (see note) but *must be completed within first 21 days following screening (Visit 0)*. See [Appendix 3](#) for a brief summary of the AGA guidelines for colonoscopy screening and surveillance for prevention of colorectal cancer.

OR,

- 2) If the patient satisfies all other Inclusion/Exclusion criteria at Screening Visit and has an unexplained and clinically significant "alarm" sign(s) or symptom(s) at Visit 1 and the Investigator determines that a colonoscopy is required to adequately assess the "alarm" sign or symptom, then a study related eligibility colonoscopy can be requested (see note) but *must be completed within 21 days following screening (Visit 0)*.

Note: If a colonoscopy is to be conducted as part of this study under either of the clinical scenarios outlined above, it will require sponsor or Medical Monitor approval, via the colonoscopy approval form. Once sponsor/medical monitor approval has been received, the procedure must be completed within 21 days following screening (Visit 0) and results must be reviewed and all findings must be negative for the presence of cancer or any of the GI conditions detailed in the exclusion criteria before the patient can be enrolled into the study.

4.3 Patient Reported Outcomes

The following patient questionnaires will be administered at the scheduled study visits:

- Patient Rating of Relief of IBS Symptoms
- Treatment Satisfaction Assessment
- Treatment Continuation Assessment

The self-administered questionnaires will be conducted during the scheduled study visits (as specified in Section 5.2), preferably prior to any other study assessments. Completion of the questionnaires takes 1 to 5 minutes. The items of the questionnaires are depicted in Appendix 1.

4.4 Safety Variables

4.4.1 Collection of Adverse Events

Adverse event (AE) collection for the study will begin immediately after the ICF is signed. All AEs occurring prior to first dose of study drug are considered medical history (MH). It is the responsibility of the Investigator to ensure that all serious and non-serious AEs are collected. For details on the assessment, reporting, recording and follow-up of adverse events, see Section 7. IBS-C is characterized primarily by abdominal pain and constipation; however, several additional symptoms are often associated with IBS-C including abdominal discomfort, abdominal bloating, incomplete evacuation and straining with bowel movements. Because IBS-C is the condition under study in this clinical trial these IBS-C related symptoms are expected over the course of a patients participation in the trial; therefore, when reported as related to IBS-C, these symptoms should not be recorded as adverse events.

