7 ASSESSMENT, REPORTING, RECORDING AND FOLLOW UP ADVERSE EVENTS

7.1 Definitions

An AE is any untoward medical occurrence associated with the use of a drug in humans, whether or not considered drug-related. An AE can therefore be any unfavorable and unintended sign (including abnormal laboratory finding), symptom, or disease temporally associated with the use of an investigational product or study procedure whether or not considered related to the product or procedure. All AEs, including intercurrent illnesses and regardless of the source of identification (e.g., PE, laboratory assessment, ECG, reported by patient), occurring during the study will be documented in the eCRF. Concomitant illnesses, which existed before entry into the study, will not be considered AEs unless they worsen (increase in intensity or frequency) during the treatment period.

Adverse events occurring from the time of ICF signing up to the intake of the first dose of study drug will be classified as pre-existing conditions for this study. Serious AEs (as defined below) occurring from the time of ICF signing up to the intake of the first dose of study medication will be collected and reported as such. A TEAE is defined as an AE that begins or that worsens in frequency and/or severity after at least one dose of study drug has been administered.

Minor fluctuations in laboratory values for standard monitoring (abnormal values) that the Investigator does not consider clinically significant or related to study drug will not be recorded as AEs. However, if the laboratory abnormality is associated with a diagnosis, then the AE term for that diagnosis will be reported (see Section 7.4 for recording of AEs).

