7.3.1 Seriousness

An SAE is defined as any untoward medical occurrence that, at any dose, is one of the following:

- Results in death;
- Is life-threatening; (an adverse event or suspected adverse reaction is considered “life threatening” if, in the view of either the Investigator or Sponsor, its occurrence places the patient or subject at immediate risk of death. It does not include an adverse event or suspected adverse reaction that, had it occurred in a more severe form, might have caused death);
- Requires inpatient hospitalization or prolongation of existing hospitalization;
- Results in a persistent or significant incapacity or substantial disruption of the ability to conduct normal life functions;
- Is a congenital anomaly or birth defect;
- Is a medically important event (Examples of such medical events include allergic bronchospasm requiring intensive treatment in an emergency room or at home, blood dyscrasias or convulsions that do not result in inpatient hospitalization or the development of drug dependency or drug abuse)

The FDA has defined additional “**Medically Important Events**” that should also be reported as SAEs [13]. These include cases where:

- Aminotransferases (ALT or AST) are ≥ 3 times the upper limit of normal (ULN) with an associated elevation of Total Bilirubin ≥ 2 times ULN without evidence of hemolysis or with alkaline phosphatase < 2 times ULN or not available OR
- ALT or AST activity that is greater than 5 times the upper limit of normal.

All patients with the above abnormalities should return as soon as possible or within 48 hours to the study center for further evaluation of the abnormalities including repeat ALT and AST, total and direct bilirubin, alkaline phosphatase, and related laboratory assessments of albumin, PT and PTT, creatinine kinase, and GGTP or 5' nucleotidase. Hepatitis A, B, and C, hemolysis, and biliary obstruction should be ruled out. A detailed medical and drug use history should be taken to exclude all potential causes.

The Medical Monitor should be consulted prior to withdrawing a patient early due to elevated ALT or AST.

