7.3.3 Causality

The Investigator will assess the causality/relationship between the study drug, or study procedure, and the AE and record that assessment in the eCRF.

The causal relationship of the AE to study drug will be described in terms of:

Reasonable Possibility: There is evidence to suggest a causal relationship between the drug and the AE (e.g., AE is uncommon and known to be strongly associated with drug exposure or is uncommon in the study population, but not commonly associated with drug exposure)

No Reasonable Possibility: There is no evidence to suggest a causal relationship between the drug and the AE.

The study conduct relatedness for AEs and SAEs will also be assessed and documented. The most likely cause of an AE or SAE (e.g., disease under treatment, concomitant disease, concomitant medication, other) will be recorded in the eCRF with details of the concomitant disease or medication or other cause.

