7.4 Recording Adverse Events

Adverse event reporting will extend from signing of ICF up to 30 days after the administration of the last dose of the study medication. Adverse events occurring after the end of the study should be reported to the Sponsor by the Investigator only if the Investigator considers there to be a causal relationship to the study drug.

All AE reports should contain a brief description of the event, date of onset, date of resolution, intensity, treatment required, relationship to study drug, action taken with the study drug, outcome of the adverse event, and whether the event is classified as serious.

All AEs experienced by patients who are assigned to treatment, regardless of the relationship to study drug, will be recorded in the eCRF.

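### Section 4.4.1 keeps listed symptoms attributed to IBS-C out of the AE record even when they begin or worsen on study drug, which conflicts with the AE and TEAE definitions in Section 7.1

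*Combined protocol and SAP*

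**What the plan says.** Section 4.4.1 names abdominal pain and constipation as the main features of IBS-C and adds discomfort, bloating, incomplete evacuation and straining. It calls these expected during participation and concludes that "when reported as related to IBS-C, these symptoms should not be recorded as adverse events". The condition is attribution alone; onset, worsening, severity and seriousness are not mentioned. The section refers to Section 7 for details of AE recording but does not say which text governs if they differ.

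Section 7.1 opens with "An AE is any untoward medical occurrence associated with the use of a drug in humans, whether or not considered drug-related". It extends this to "any unfavorable and unintended sign (including abnormal laboratory finding), symptom, or disease temporally associated with the use of an investigational product". A TEAE is "an AE that begins or that worsens in frequency and/or severity after at least one dose of study drug".

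Section 7.4 adds that "All AEs experienced by patients who are assigned to treatment, regardless of the relationship to study drug, will be recorded in the eCRF". Section 7.3.3 says that "The most likely cause of an AE or SAE (e.g., disease under treatment, concomitant disease, concomitant medication, other) will be recorded in the eCRF".

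Section 2.4.1 measures safety and tolerability first by the number and nature of TEAEs. Section 8.8 uses AE-free days as a tolerability measure. Section 8.9 lists all AEs but restricts the summary tables to TEAEs.

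**The concern.** The two sections apply different tests. Section 4.4.1 asks what the symptom is blamed on; Section 7.1 asks when it began or worsened. Non-serious abdominal pain that increases after dosing and is put down to the underlying disease meets the Section 7.1 definition of a TEAE but may not be recorded under Section 4.4.1. Two sites could handle the same event differently, and each could point to the protocol.

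Safety and tolerability is the primary objective, and there is no control arm. Whether a change in a listed symptom reflects the disease or the drug is the judgement such a design supports least well. Section 4.4.1 lets that judgement decide whether the event enters the data at all. An event that is never recorded as an AE is missing from the listings as well as the tables, so no later analysis can restore it.

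**Working it through.** The plan gives no figure to reproduce: Section 8.2 says that power calculations do not apply. The check is a comparison of texts followed by an argument on direction.

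**Step 1: where the sections agree and differ.**

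| Listed symptom | Section 4.4.1 | Section 7 |
|---|---|---|
| Present at entry, stable, attributed to IBS-C | Not recorded | Not treatment-emergent under 7.1 |
| New or worse after first dose, attributed to IBS-C, not serious | Not recorded | Meets the 7.1 AE and TEAE definitions |
| New or worse, attributed to study drug or another cause | Bar does not apply | Recorded |
| Meets a seriousness criterion | No exception stated | Largely covered by 7.3.1 and 7.5 |

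The conflict lies in the second row. In the fourth row, Section 7.3.1 begins "An SAE is defined as any untoward medical occurrence that, at any dose, is one of the following", and Section 7.5 requires SAEs to be reported regardless of causal relationship to study medication. Only the silence of 4.4.1 needs repair there.

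**Step 2: weight of the other passages.** Section 7.4 applies once something counts as an AE, and its wording concerns relationship to study drug rather than to IBS-C. It is supporting evidence. In Section 7.3.3, having the disease under treatment among the possible causes implies that some disease-caused events are recorded, but does not order it. The worsening clause in Section 7.1 is worded for concomitant illnesses, so it too is only support.

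**Step 3: direction.** Let p be the share of patients with a new or worsened listed symptom, and f the share of those patients for whom it goes unrecorded because it was attributed to IBS-C. For the same patients and events:

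- Recorded incidence = p × (1 − f). With f between 0 and 1, this never exceeds p.
- Person-time rate, counting first events: removing events lowers or preserves the numerator and lengthens or preserves time at risk, so the rate cannot rise. With total exposure as denominator, only the numerator can change, and the result is the same.
- AE-free days: a day whose only event is an unrecorded symptom counts as AE-free, so the total stays the same or rises.

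**Step 4: size.** The documents give neither p for these symptoms in IBS-C nor any value for f. Section 2.1.3 reports abdominal pain and distension among TEAEs in at least 2% of patients in the phase 2b CIC trial. That is a different population and says nothing about f. Any numerical range would consist of assumptions only, so none is given.

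**Step 5: is there a baseline against which to judge worsening?** In Tables 3 and 4 the medical history row covers new information not already held from the core study, and the questionnaires begin at Week 4. Sections 5.2.2.1 and 5.2.2.2 list no symptom grading at baseline. Section 8.7.1 has the relief rating collected at all visits, but it is one overall score. Rome III is not required of patients randomised in the core studies and has no item on bloating or straining. No graded entry status for each listed symptom is specified.

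**The case against.** The best defence is that 4.4.1 is a deliberate, specific rule qualifying a general definition, much as Section 7.2 does for diarrhea. IBS-C fluctuates, and recording every return of pain or constipation would put loss of effect into the safety tables. The rationale is sound for expected symptoms. It does not extend to deterioration on study drug, and Section 7 nowhere restates or limits the exclusion. The diarrhea rule also keeps a route to recording, since the patient can call the event bothersome; 4.4.1 has none for a non-serious listed symptom attributed to IBS-C.

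Other routes may reveal deterioration: the overall relief rating, the recorded withdrawal reasons, and the Section 5.2.5 text treating clinically significant changes in assessments as AEs for which participation may end. These are partial. The rating does not identify the symptom, the Section 5.2.5 text concerns termination and does not name symptoms, and neither the rating nor a withdrawal reason puts an unrecorded symptom into the TEAE tables. The eCRF completion guidelines mentioned in Section 9.1.1 may also bear on recording, but are not among the documents reviewed.

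A reader might infer more than the text supports:

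- That drug-caused symptoms are barred. They are not; the bar depends on attribution to IBS-C.
- That 4.4.1 directly contradicts 7.4. It does not, because 7.4 presupposes an AE.
- That serious events are lost. Sections 7.3.1 and 7.5 largely cover them.
- That the understatement is known to be large. Nothing in the documents shows its size.

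**Conclusion.** The point holds for non-serious listed symptoms that begin or worsen after the first dose and are attributed to IBS-C. For these, 4.4.1 and 7.1 give opposite instructions. The effect runs one way: recorded TEAE rates for the listed symptoms are lowered or unchanged, and AE-free days are raised or unchanged. The affected terms are not only abdominal ones, because constipation, straining and incomplete evacuation are on the list. The size is unknown. The conclusion on direction assumes that sites follow 4.4.1 as written, and compares the same events with and without the rule. It should be fixed, because the affected counts serve the primary objective and no control arm would show what is missing.

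**What to change.** Replace the final sentence of 4.4.1 with text to this effect: listed IBS-C symptoms present at study entry that have not worsened are not recorded as AEs. A listed symptom is recorded as an AE, with its suspected cause captured under 7.3.3, if it newly appears after the first dose in this study, if in the investigator's judgement it becomes more intense or more frequent after that dose, or if it meets a 7.3.1 seriousness criterion.

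Have the investigator note the status of each listed symptom at entry in the source or medical history record. The present schedule should not be assumed to supply this.

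The cost is a short amendment, with IRB approval where appropriate under Section 9.8, a site memo and a brief extra entry at baseline. There are three downsides:

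- More disease fluctuation and loss of effect will be recorded, including in patients who roll over directly from active treatment. The cause field helps identify such events but, without a control arm, cannot fully separate them from drug effect.
- The threshold for worsening rests on judgement, as it already does in 7.1.
- If patients are already enrolled, the data will contain two recording periods. These must be identified when TEAE rates are summarised.

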4.4.2 Clinical Laboratory Variables

Clinical laboratory assessments will be performed by a central laboratory, as identified in the List of Study Personnel and Vendors. The Laboratory Manual provided to investigative sites includes detailed instructions regarding the collection, processing, and handling of laboratory samples, including those for immunogenicity testing.

6 to 12-hour fasting is recommended before laboratory assessments are performed. The laboratory variables presented in **Table 2** will be assessed in accordance with the Schedule of Assessments (**Table 3 or Table 4**, as applicable).

Approximately 2.0 mL of blood will be drawn for each hematology sample, 5.0 mL for each serum chemistry sample, and 3.5 mL for each immunogenicity sample. The total blood volume collected from each patient for laboratory tests, not including possible repeat tests, over the course of 53 weeks will be approximately 60 mL.

Table 2: Clinical Laboratory Assessments

Hematology	Erythrocytes, mean corpuscular volume (MCV), mean corpuscular hemoglobin (MCH), neutrophils, eosinophils, basophils, lymphocytes, monocytes, platelets, leukocytes, hemoglobin, and hematocrit
Serum chemistry	Alanine aminotransferase, aspartate aminotransferase, creatinine, alkaline phosphatase, total bilirubin, direct bilirubin, blood urea nitrogen, total protein, albumin, uric acid, glucose and cholesterol Electrolytes: Sodium, potassium, chloride, magnesium, phosphorus, calcium
Urinalysis	Specific gravity, pH, protein, glucose, ketones, blood, and microscopic examination of sediment
Urine Pregnancy test	Pregnancy test via dipstick (performed at study site for women of childbearing potential)
Urine Drug Screen	Urine tests for methadone, morphine and oxycodone (performed at study site)
Immunogenicity	Serum collection for anti-plecanatide antibodies testing (samples will be stored until an assay is developed)

4.4.3 Vital Signs

Vital sign measurements will be performed after the patient has been seated for at least 5 minutes. The following vital signs will be performed in accordance with the Schedule of Assessments (**Table 3 or Table 4**, as applicable):

- Blood pressure (systolic and diastolic; mmHg)
- Heart rate (beats per minute)
- Body temperature (°C)
- Respiration rate (breaths per minute)

4.4.4 Electrocardiograms

Standard 12-lead ECGs will be performed in accordance with the Schedule of Assessments (**Table 3 or Table 4**, as applicable).

All ECGs will be performed in either the supine or semi-recumbent position.

4.4.5 Physical Examinations

Physical examinations will be performed in accordance with the Schedule of Assessments (**Table 3 or Table 4**, as applicable). The PE will be based on the following body systems: general appearance, head (ear, eyes, nose, and throat), cardiovascular, respiratory, abdomen, musculoskeletal, neurological, lymph nodes, and skin.

4.4.6 Concomitant Medications and Diet

Any new or changes to concomitant medications and dietary supplements will be documented at each study visit. Any clinically significant change in medications or dietary intake/supplements that could adversely affect the patient or study should be documented by the site and discussed with the Medical Monitor to determine whether the patient should continue in the study.

